- Intercurrent illness that may compromise the patient's life or interfere with the treatment study evaluation
- Requirements for concomitant medication that may interfere with study results.
- Failure to complete the study entirely
- Failure to follow up on the patient.

Sample Size

Recruitment will be conducted to terminate the study after a specific number of patients have been enrolled if a minimum number of responses have not been observed. The lowest significant response rate will be 20% ($\alpha = 0.10$; $\beta = 0.10$). If at least the minimum number of objective responses are observed to complete recruitment, 30 evaluable patients will be enrolled. For example, if there is no response in any of the first 12 treated patients or only 1 out of the first twenty, the study should be terminated. The confidence interval for the response rate is $>20\%$.

Evaluable Patient: An evaluable patient meets the inclusion criteria, does not meet any of the removal criteria, receives all four vaccination cycles, and has been clinically and radiologically followed until the end of this trial.

Study Conduct

- Signing of informed consent
- Complete medical history
- Complete physical examination
- Karnofsky Performance Status measurement
- Estimation of survival quality using the EORTC scale
- If applicable, photographs of the tumor and metastases
- Hematological studies, including albumin and total proteins.
- Electrocardiogram
- CD3, CD4, CD8 cell counts, and total lymphocyte count
- Blood sample collection for in vitro immunological studies.
- Staging radiological studies: Computed tomography of the brain, lungs, abdomen, and pelvis, and bone scintigraphy
- Estimation of metastasis size through physical and radiological examination
- Delayed hypersensitivity test (DTH)

Enrollment

After the procedures mentioned above, each eligible patient will be enrolled. Each patient will be given an identification number. Data will be maintained in a computerized file with restricted access for the research team for each patient.

Patient Monitoring

Patients will be clinically monitored once a week through the following parameters:

- Weight
 - Karnofsky Index
 - Vital signs
 - EORTC Quality of Life Index
 - Comprehensive physical examination
 - Monitoring for toxicity symptoms according to WHO Criteria Grading Toxicities and reporting adverse effects

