- Additionally, they will be evaluated through ELISPOT and ELISA assays, with blood samples taken before each vaccination, to assess the response of specific CTLs to DC stimulation and the presence of cytokines in the patient's serum.

Measurement at the End of Treatment

- Clinical evaluation of the patient
- Estimation of clinical or radiological tumor response: determining tumor volume
- Comprehensive physical examination
- Karnofsky Index
- Photography
- Quality of life and pain assessments
- Delayed hypersensitivity test (DTH): for in vivo response measurement
- Hematological and chemical tests: Assays for measuring in vitro immune response.

Long-Term Follow-Up

Once the patient has completed the full four-cycle treatment, they must be followed up every four weeks for one year. Every two months during the second year. The date of death must be determined in applicable cases. During each visit:

- Directed physical examination
 - Karnofsky Index
 - Estimation of clinical and radiological tumor size
 - Photography
 - EORTC Quality of Life Assessment
 - Reporting of adverse effects
- Clinical Response Assessment

TUMOR RESPONSE CRITERIA

CR: Complete disappearance of the tumor

PR: Tumor regression > 50%

MR: Tumor regression > 25% - <50%

SD: Decrease or growth < 25%

PD: Increase in tumor size during treatment

Statistical Analysis

The primary objective of this study is to estimate the objective response and toxicity associated with treatment using dendritic cells loaded when administered to patients with disseminated melanoma. A stratified recruitment design will be used in this study. In the first stage, 12 patients will be enrolled and treated with loaded dendritic cells. If none of the patients responds to the treatment, enrollment for this study will be terminated. If at least one patient responds to the treatment, the treatment will continue. If, after the enrollment of patient number 20, at least two patients respond to the treatment, the study should continue until a minimum of 30 evaluable patients with 3 out of 4 completed cycles. Assuming that the study will be completed with thirty patients as planned, the 90% confidence interval for the estimated response rate will be 12%, assuming a 20% response rate. If sufficient evidence indicates that the valid response rate is greater than 20%, it would be given if the lower limit of the confidence interval is more significant than 0.20 (alpha = 0.05, 1-tailed -test).

Primary Efficacy Analysis

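### The stable and progressive disease definitions overlap for on-treatment growth above 0% and below 25%, and read literally, larger growth in follow-up has no category

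*Protocol*

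**What the plan says.** The protocol's Tumor Response Criteria list five categories. Complete response is disappearance of the tumour. The other four are:

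- "PR: Tumor regression > 50" (per cent)
- "MR: Tumor regression > 25% - <50" (per cent)
- "SD: Decrease or growth < 25" (per cent)
- "PD: Increase in tumor size during treatment"

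Tumour burden is assessed at three kinds of visit:

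- Before treatment (Study Conduct): "Estimation of metastasis size through physical and radiological examination".
- At the end of treatment: "Estimation of clinical or radiological tumor response: determining tumor volume".
- At each Long-Term Follow-Up visit: "Estimation of clinical and radiological tumor size". After treatment, patients are seen on this schedule: "they must be followed up every four weeks for one year. Every two months during the second year".

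Of the response categories, the clinical response aim reports only the percentages with complete and partial response. The Sample Size and Statistical Analysis sections stop enrolment if there is no response in the first 12 patients, or only one in the first 20.

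**The concern.** A response scale should give each assessment exactly one label. Here the progression line has no lower limit, while the stable-disease line admits growth up to 25%. A patient whose tumour grows by 10% during treatment satisfies both, and the text available gives no order of precedence.

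The progression line also applies only during treatment. Tumour size continues to be estimated for two years afterwards, so the scale has no literal label for substantial growth at those visits.

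At stake are the consistency of the stable and progressive disease counts and any descriptive account of the course after treatment. These counts would depend on which of two adjacent lines an assessor chose to apply.

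**Working it through.** There is no sponsor figure to reproduce, because the point is one of logic. The inputs are the five definitions as printed. Write *c* for percentage change in tumour measure, negative for regression. The stable-disease limit of 25% is taken to apply to decrease as well as growth; the overlap with progression is the same if it applies to growth only.

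The list then reads:

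- CR: *c* = −100
- PR: −100 < *c* < −50
- MR: −50 < *c* < −25
- SD: −25 < *c* < +25
- PD: *c* > 0, on treatment only

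**Overlap on treatment.** SD and PD hold together when *c* > 0 and *c* < +25. On a 1-point grid from −100% to +100% the doubly labelled values are +1% to +24%, which is 24 values. No other pair of categories overlaps.

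**Gap in follow-up, read literally.** Without PD, nothing covers *c* ≥ +25. On the same grid that is +25% to +100%, or 100 − 25 + 1 = 76 values.

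**Ties.** *c* = −50 and *c* = −25 fall in no category in either period, because the inequalities are strict on both sides.

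| Change | On treatment | Follow-up (literal) |
|---|---|---|
| −75% | PR | PR |
| −40% | MR | MR |
| −10% | SD | SD |
| +10% | SD and PD | SD |
| +24% | SD and PD | SD |
| +25% | PD | none |
| +40% | PD | none |

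If the limit to the treatment period is instead ignored, the gap closes but the overlap between 0% and 25% extends to follow-up. Neither reading gives one label per assessment.

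**Effect on the primary rate.** CR and PR require regression above 50%. The overlap lies wholly at *c* > 0. Moving a patient between SD and PD therefore leaves CR + PR unchanged, and with it the counts used at 12 and 20 patients.

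**The case against.** The strongest reply is that the intention is plain: progression must mean growth beyond the stable-disease limit, and any sensible assessor would read it so. That is a reasonable guess, and the repair below adopts it as the simplest option. But the printed line says otherwise, and an assessor who calls 10% on-treatment growth progression is also following the text.

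A second reply is that a statistical analysis plan may settle precedence. It may. The protocol nevertheless fixes both definitions itself and fixes them inconsistently, so this is a contradiction rather than detail left for later.

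A third reply concerns follow-up. The line on clinical response assessment may be a heading for the criteria rather than a follow-up procedure, and no stated endpoint is shown to use a progression label from follow-up. This stands and limits the consequence. Estimation of tumour size at those visits is explicit either way.

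A reader might also infer more than the documents support:

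- *That the response rate or the early stopping rules are distorted.* The overlap lies entirely in the growth range, so it cannot by itself move a patient into or out of CR or PR.
- *That the measure behind the percentages is open, because some visits record size and one records volume.* The end-of-treatment section ties response to volume, size is a general word, and no competing measure such as diameter is named. One clarifying sentence is worthwhile, but no contradiction is shown.
- *That the ties at exactly 25% and 50% matter.* On a continuous measure they are trivial.
- *That silence on new lesions is an error.* It is an omission of a kind that an analysis plan commonly covers.
- *That the progression label decides who receives further doses, and so who is evaluable.* The Treatment section makes the next dose depend on the absence of evident progression but does not link this to the PD line. The two places need reconciling; an effect on the denominator cannot be asserted.

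**Conclusion.** The point holds as a minor error in a stated rule. For all on-treatment growth above 0% and below 25%, the text assigns both stable and progressive disease without precedence. Read literally, follow-up growth of 25% or more has no category. The consequence is unreliable SD and PD counts; CR + PR and the 12- and 20-patient rules are unaffected by the overlap itself.

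The conclusion needs no assumption about sample size, error rates or response rate. It rests on the printed definitions and on the absence of a precedence rule in the text available. The documents give no basis for estimating how many patients would fall in the overlapping range, so no number of affected patients is claimed.

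**What to change.** For endpoint classification only, make the categories mutually exclusive and exhaustive at every assessment, on treatment and in follow-up, by change from the pre-treatment value:

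- **SD:** keep as a change below 25% in either direction.
- **PD:** make it the complement, growth of 25% or more, and delete the limit to the treatment period. The list gives PD no percentage of its own, so this boundary is borrowed from the SD line. The sponsor may set another single SD/PD boundary, provided it is fixed before any response is read.
- **Ties:** give exactly 25% and exactly 50% regression one category each. Placing both in MR leaves the PR and SD lines as printed.
- **Measure:** state that the percentages refer to tumour volume, the measure the protocol names for response, at all visits.

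With these changes the ranges −100, (−100, −50), [−50, −25], (−25, +25) and +25 upward cover every value once.

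A secondary and inexpensive improvement is to state that a patient with a new lesion at an assessment is not counted as CR or PR there, and to name the category that applies instead. The downside is that the response rate may be slightly lower.

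The cost is a few rewritten lines. Volume would have to be derived before treatment and in follow-up, where size is already estimated. Because change is measured from the pre-treatment value, regrowth after a response would be labelled PD only once it exceeds that value by the chosen margin.

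Separately, the sponsor must reconcile the reference to evident progression among the next-dose conditions in the Treatment section with the PD definition. No dosing or stopping rule is proposed here.
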